9.2. Clinical Laboratory Evaluations

Laboratory assessments will be performed by a central laboratory. All summaries will be based on the units provided by the central laboratory (ie, no conversion will be done).

9.2.1. Hematology

The following laboratory tests will be included: hemoglobin (including mean corpuscular volume), mean corpuscular hemoglobin, mean corpuscular hemoglobin concentration, hematocrit, red blood cell count, total white blood count, platelet count, differential blood counts, including basophils, eosinophils, neutrophils, lymphocytes, and monocytes.

Summary tables presenting observed values and changes from baseline will be presented for hematologic tests with numeric values by treatment group for subjects in the Safety Analysis Set. Changes from baseline to each scheduled post-baseline visit will be presented. All hematology data by subject will also be presented in a listing.

The clinical assessment of ‘Low’, ‘Normal’, or ‘High’ relative to the reference range will be summarized in shift tables comparing the baseline results to maximum value post-baseline for those subjects with results at both visits.

All hematology data by subject will be presented in a listing.

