Under FIS-002-2019 protocol version 3.0, the randomized, double-blinded, placebo-controlled portion of the study was scheduled to end at Week 24 with all primary endpoint visits completed by week 16. The COVID-19 pandemic has had a significant impact on the conduct of this clinical trial leading to many missing Week 16 and Week 24 visits and preventing the rolling over to the long-term OLE part of the study. Research site closures and individual study subjects have already missed visits and Fulcrum anticipates that many others will be missed unless rapid corrective actions are implemented. In addition, the necessary pandemic restrictions limit the assessment of long-term safety in the FSHD1 population in the clinic, as well as collection of critically important efficacy data on Week 24 on clinical outcome assessments and MRIs. Further, the investigational drug delivery that currently takes place during the clinic visits is also now compromised, resulting in the potential for treatment gaps unless home delivery is rapidly enabled.

Fulcrum Therapeutics

Losmapimod

Protocol FIS-002-2019, Version 4.0 (COVID-19 Pandemic Emergency Amendment)

10 April 2020

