6.2.2 Laboratory Analyses

Samples for serum chemistry, hematology, coagulation, and urinalysis will be collected at the time points specified in [Table 13-1](#) and [Table 13-2](#). Processing, storage, and shipping

Fulcrum Therapeutics Losmapimod
Protocol FIS-002-2019, Version 4.0 (COVID-19 Pandemic Emergency Amendment) 10 April 2020
procedures for all clinical laboratory samples are provided in a laboratory manual. Sample collection details are presented in [Section 6.7](#).

For the screening visit, subjects will be required to fast for at least 4 hours prior to laboratory blood samples being taken.

Any abnormal laboratory test results (hematology, clinical chemistry, or urinalysis) or other safety assessments (eg, ECGs, radiological scans, vital sign measurements), including those that worsen from baseline (ie, prior to first dose in the placebo-controlled treatment period) and are felt to be clinically significant in the medical and scientific judgment of the investigator, are to be recorded as AEs or SAEs. However, any clinically significant safety assessments that are associated with the underlying disease, unless judged by the investigator to be more severe than expected for the subject's condition, are **not** to be reported as AEs or SAEs. Clinically significant abnormal laboratory test results will be reviewed by the investigator and recorded as AEs or SAEs on the appropriate page in the eCRF.

Fulcrum Therapeutics

Losmapimod

Protocol FIS-002-2019, Version 4.0 (COVID-19 Pandemic Emergency Amendment)

10 April 2020

Blood and other biological samples will be collected for the following clinical laboratory tests:

Serum chemistry	Glucose, sodium, potassium, calcium, inorganic phosphate, total protein, albumin, blood urea nitrogen, creatinine, total bilirubin, alkaline phosphatase, aspartate aminotransferase, alanine aminotransferase, gamma-glutamyltransferase, creatine phosphokinase
Hematology	Hemoglobin (including mean corpuscular volume), mean corpuscular hemoglobin, mean corpuscular hemoglobin concentration, hematocrit, red blood cell count, total white blood cell count, platelet count Differential blood counts, including basophils, eosinophils, neutrophils, lymphocytes, and monocytes
Coagulation	International normalized ratio, prothrombin time, partial thromboplastin time

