4.1. Reporting Conventions

All data summaries, unless otherwise noted, will be presented by treatment group:

- Losmapimod 15 mg BID
- Placebo BID

The following conventions will be used for all the data presentations and analyses unless otherwise specified.

Appropriate descriptive statistics will be computed and displayed for both continuous and categorical variables. For continuous and quantitative variables, summaries will include n (number of subjects with non-missing data), mean, standard deviation (SD), Q1 (first quartile), Q3 (third quartile), median, minimum and maximum. Reporting conventions for descriptive statistics will follow the [REDACTED] Standard TLF Guidelines. For categorical variables, summaries will include the number and percentage of subjects who are in a particular category. Percentages will be computed based on the number of non-missing data points for patients in the applicable analysis set. Reporting of percentages will follow the [REDACTED] standard TLF Guidelines.

A total column will be presented for all demographic, baseline characteristic, baseline disease characteristic, protocol deviation, and prior and concomitant medication summaries.

All data will be listed by treatment group, FSHD repeat number category, subject ID, Ricci score, sex and visit date, if available. Any repeat assessments or additional assessments, along with any unscheduled visits, will be presented in the listings. Sort order of data listings will be treatment group, FSHD repeat number category, subject ID, and visit date, if available.

Statistical tests will be 2-sided and will be conducted at the significance level provided in [Table 12-1](#)), unless otherwise specified. P-values will be reported to 4 decimal places, with p-values less than 0.0001 reported as “<0.0001”.

All analyses will be performed using Statistical Analysis Software (SAS®, release 9.4 or higher). A separate document as an appendix to this SAP will contain the tables, listings, and figure (shells).

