9.2.2. Serum Chemistry

The following laboratory tests will be included: glucose, sodium, potassium, calcium, inorganic phosphate, total protein, albumin, blood urea nitrogen, creatinine, total bilirubin, alkaline phosphatase, aspartate aminotransferase, gamma-glutamyl transferase, and creatinine phosphokinase.

Summary tables presenting observed values and changes from baseline will be presented for serum chemistry tests with numeric values by treatment group for subjects in the Safety Analysis Set. Changes from baseline to each scheduled post-baseline visit will be presented. All chemistry data by subject will also be presented in a listing.

The clinical assessment of ‘Low’, ‘Normal’, or ‘High’ relative to the reference range will be summarized in shift tables comparing the baseline results to maximum value post-baseline for those subjects with results at both visits.

Results indicating liver-related abnormalities (i.e., ALT, AST, Total Bilirubin, and/or Alkaline Phosphatase) will also be summarized separately. A newly notable laboratory abnormality is defined as an abnormality observed post baseline that meets the notable criteria in [Table 9-1](#) and that did not exist at baseline. Subjects can still meet the criteria for a newly notable laboratory abnormality if the baseline value is missing. The table below displays the general variables and thresholds of interest. Subjects are considered to have notable laboratory abnormalities if his/her response falls within the specified definitions at least once during the treatment period.

Table 9-1: Notable Criteria for Laboratory Data Abnormalities – Liver Function Tests

Laboratory Variable	SI Units
AST	$\geq 3 \times \text{ULN}$
ALT	$\geq 3 \times \text{ULN}$
Total Bilirubin	$\geq 2 \times \text{ULN}$
Alkaline Phosphatase (ALP)	$\leq 2 \times \text{ULN}$
ALT or AST $> 3 \times \text{ULN}$ and total bilirubin $> 2 \times \text{ULN}$ and ALP $< 2 \times \text{ULN}$ (potential DILI or Hy's law case)	

All chemistry data by subject will be presented in a listing.

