Table	14.3.1.4.1	Treatment-Emergent Adverse Events by Maximum Severity	Open-label losmapimod (Pre-COVID-19) Analysis Set	R	9.1.3	Safety		
Table	14.3.1.5	Treatment-Emergent Adverse Events Leading to Treatment Discontinuation by System Organ Class and Preferred Term	Safety Analysis Set	R	9.1.5	Safety		
Table	14.3.1.5.1	Treatment-Emergent Adverse Events Leading to Treatment Discontinuation by System Organ Class and Preferred Term	Open-label losmapimod (Pre-COVID-19) Analysis Set	R	9.1.5	Safety		
Table	14.3.1.6	Treatment-Emergent Adverse Events Leading to Study Withdrawal by System Organ Class and Preferred Term	Safety Analysis Set	R	9.1.6	Safety		
Table	14.3.1.6.1	Treatment-Emergent Adverse Events Leading to Study Withdrawal by System Organ Class and Preferred Term	Open-label losmapimod (Pre-COVID-19) Analysis Set	R	9.1.6	Safety		
Table	14.3.2.1	Serious Treatment-Emergent Adverse Events by System Organ Class and Preferred Term	Safety Analysis Set	R	9.1.4	Safety		

TLF	Table Number	Title	Analysis Set	Unique (U)/Repeat (R)	Section	Efficacy/Safety/Standard	Topline	IA
Table	14.3.2.1.1	Serious Treatment-Emergent Adverse Events by System Organ Class and Preferred Term	Open-label losmapimod (Pre-COVID-19) Analysis Set	R	9.1.4	Safety		
Table	14.3.2.2	Adverse Events Leading to Death by System Organ Class and Preferred Term	Safety Analysis Set	R	9.1.7	Safety		
Table	14.3.2.2.1	Adverse Events Leading to Death by System Organ Class and Preferred Term	Open-label losmapimod (Pre-COVID-19) Analysis Set	R	9.1.7	Safety		
Table	14.3.4.1.1	Change from Baseline in Hematology	Safety Analysis Set	U	9.2.1	Safety		
Table	14.3.4.1.1.1	Change from Baseline in Hematology	Open-label losmapimod (Pre-COVID-19) Analysis Set	R	9.2.1	Safety		
Table	14.3.4.1.2	Shift from Baseline in Hematology	Safety Analysis Set	U	9.2.1	Safety		
Table	14.3.4.1.2.1	Shift from Baseline in Hematology	Open-label losmapimod (Pre-COVID-19) Analysis Set	R	9.2.1	Safety		
Table	14.3.4.2.1	Change from Baseline in Chemistry	Safety Analysis Set	R	9.2.2	Safety		
Table	14.3.4.2.1.1	Change from Baseline in Chemistry	Open-label losmapimod (Pre-COVID-19) Analysis Set	R	9.2.2	Safety		
Table	14.3.4.2.2	Shift from Baseline in Chemistry	Safety Analysis Set	R	9.2.2	Safety		
Table	14.3.4.2.2.1	Shift from Baseline in Chemistry	Open-label losmapimod (Pre-COVID-19) Analysis Set	R	9.2.2	Safety		
Table	14.3.4.2.3	Summary of Clinically Notable Laboratory Results by Visit - Chemistry (Liver)	Safety Analysis Set	U	9.2.2	Safety		

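### Laboratory shift tables use only the post-baseline maximum, so shifts to Low are undercounted; Table 9-1 also counts a normal ALP as notable

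*SAP*

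**What the plan says.** **Shift rule.** For hematology (SAP 9.2.1), the category relative to the reference range is "summarized in shift tables comparing the baseline results to maximum value post-baseline for those subjects with results at both visits". SAP 9.2.2 repeats this for serum chemistry: "shift tables comparing the baseline results to maximum value post-baseline for those subjects with results at both visits". The table list in SAP 15.8 has one such table for each panel, "Shift from Baseline in Hematology" (14.3.4.1.2) and "Shift from Baseline in Chemistry" (14.3.4.2.2), each repeated on the open-label pre-COVID-19 set. Neither that list nor the SAP addendum adds a shift to the minimum.

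**Other laboratory output.** By-visit summaries include "Q1 (first quartile), Q3 (third quartile), median, minimum and maximum" (SAP 4.1), and all results are listed by subject. Protocol 6.2.2 adds: "Clinically significant abnormal laboratory test results will be reviewed by the investigator and recorded as AEs or SAEs".

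**Liver criteria.** SAP Table 9-1 gives ALP at or below 2×ULN its own row, next to the AST, ALT and bilirubin rows, and then a combined potential drug-induced liver injury (DILI) row that also contains ALP below 2×ULN. SAP 9.2.2 states: "Subjects are considered to have notable laboratory abnormalities if his/her response falls within the specified definitions at least once during the treatment period". It also defines a newly notable result as one that was not present at baseline, and lets a missing baseline qualify. Protocol 6.2.1.3 uses ALP below 2×ULN only as one of three criteria that must all be met.

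**The concern.** The maximum suits tests where a rise is the worry, such as the transaminase and creatinine rises discussed in Protocol 1.5. It works against tests where a fall is the worry: hemoglobin, white cells, neutrophils, lymphocytes, platelets, albumin, sodium and potassium. Protocol 1.5 also raises a theoretical effect on immunity, so white-cell falls are of interest here.

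The shift table is where a reader counts, by arm, how many subjects went from Normal to Low. Under this rule the cell misses everyone who was Low at some visits but not all, including every transient fall. The gap matters most when only a minority of subjects fall, because the mean change at each visit is then modest.

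The ALP row adds to the liver table a count that is either close to 100% or points the wrong way.

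**Working it through.** The plan states no figure for this rule, so there is nothing to reproduce. Step 1 is logic; steps 2 and 3 are illustrations.

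**1. What the rule implies.** With post-baseline values x₁…x_k and lower limit L, max(x) < L holds only if every xᵢ < L. The maximum rule therefore counts subjects who are Low at all k visits; a minimum rule counts those Low at one or more. If visits were independent with a 5% Low rate and k = 6, the two proportions would be 0.05⁶ = 1.6×10⁻⁸ and 1 − 0.95⁶ = 26.5%. Visits within a subject are correlated, so step 2 allows for that.

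**2. Correlated visits.**
- From the documents: six on-treatment post-baseline visits (Weeks 4, 12, 16, 24, 36 and 48; Protocol Table 13-1). Attendance was incomplete: Protocol 3.2.2 describes the pandemic as "leading to many missing Week 16 and Week 24 visits". Three attended visits are therefore also tried.
- Assumed: normal values with total variance 1; Low below −1.96; baseline within ±1.96; intraclass correlation (ICC) 0.5, 0.7 or 0.85; and the size of the fall δ.
- Model: X_ij = √ICC·b_i + √(1−ICC)·e_ij, minus δ after baseline, with 1 to 2 million simulated subjects per setting.

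| Visits | Fall | Low at all visits (maximum rule), ICC 0.5 / 0.7 / 0.85 | Low at one or more (minimum rule) |
|---|---|---|---|
| 6 | none | 0.0001 / 0.0003 / 0.0005 | 0.094 / 0.068 / 0.043 |
| 6 | 2 SD | 0.144 / 0.224 / 0.310 | 0.878 / 0.804 / 0.723 |
| 6 | 3 SD, one visit only | 0.0002 / 0.0005 / 0.0008 | 0.859 / 0.864 / 0.868 |
| 3 | none | 0.0009 / 0.0017 / 0.0020 | 0.055 / 0.042 / 0.029 |
| 3 | 2 SD | 0.258 / 0.316 / 0.377 | 0.772 / 0.714 / 0.656 |
| 3 | 3 SD, one visit only | 0.0032 / 0.0040 / 0.0040 | 0.858 / 0.864 / 0.868 |

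The loss is not confined to single excursions. After a 2 SD fall, of subjects Low at three or more of six visits, 76 / 61 / 44% would still not be shown as Low. Of those Low at two or more of three visits, it is 50 / 39 / 27%.

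**3. Only some subjects fall.** Take 40 per arm (80 enrolled, 1:1), all assumed Normal at baseline, with 20% of one arm (8 subjects) falling 2 SD. Excess over the other arm = 8 × (proportion with fall − proportion without).
- Six visits, maximum rule: 8 × (0.144 − 0.0001) = 1.2 to 8 × (0.310 − 0.0005) = 2.5 subjects.
- Six visits, minimum rule: 8 × (0.723 − 0.043) = 5.4 to 8 × (0.878 − 0.094) = 6.3 subjects.
- Three visits, by the same formula: 2.1 to 3.0 against 5.0 to 5.7 subjects.

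The mean difference at a visit is 0.2 × 2 = 0.4 SD. Its SE is √{[2(1−ICC) + 0.2×0.8×2²]/40 + 2(1−ICC)/40} = 0.257 / 0.214 / 0.176, so the difference is 1.6 / 1.9 / 2.3 SE.

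**4. The ALP row.** An ALP at 1×ULN meets the printed criterion; one at 3×ULN does not.
- Read as notable (met once), nearly every subject qualifies.
- Read as newly notable, anyone at or below 2×ULN at baseline is excluded. The remaining hits are subjects whose ALP came down from above 2×ULN, or whose baseline is missing.

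A true rise is flagged under neither reading.

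**The case against.** The case against giving this much weight is reasonable. No hypothesis test depends on it. Low values remain visible in by-visit quartiles and minima, in listings and in adverse events. Protocol 7.6.6 asks only for descriptive summaries over time, so shift tables go beyond it. The fall sizes are assumed, and the protocol names no expected fall in a blood count, albumin or electrolyte. In the partial-fall example a mean difference of 1.6 to 2.3 SE at each visit is not hidden. The table shells are a separate document and might carry a minimum. A minimum rule also has a price: over the 27 tests in SAP 9.2.1 and 9.2.2, with 40 subjects and six visits, chance Low entries come to 27 × 40 × 0.043 = 46 to 27 × 40 × 0.094 = 102 per arm. The ALP row could be read as a component of the combined criterion, and a count near 100% would be obvious.

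This limits the consequence but does not repair the count. A by-visit minimum shows one extreme value, not how many subjects fell, and adverse events depend on the investigator's judgement. The shells cannot be seen, and the SAP text says maximum. The chance entries are expected equally in both arms and shrink if the minimum is limited to tests where a fall matters. For the eight named under the concern they are 8 × 40 × 0.043 = 14 to 8 × 40 × 0.094 = 30 per arm. The text gives the ALP row as a criterion in its own right.

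**Conclusion.** Both points hold. That the maximum rule shows a subject as Low only when all post-baseline values are Low follows from the wording and needs no assumption. The size of the undercount is illustrative and depends on the assumed normality, correlation, fall size and attendance. For a uniform 2 SD fall, 14-31% are shown as Low against 72-88% with any Low value (six visits), or 26-38% against 66-77% (three visits). A fall at one visit only is almost never counted.

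The damage is confined to the categorical safety count. Low values are not lost from the report, and efficacy inference is untouched. Coagulation is unaffected in practice: SAP 9.2.4 points to the 9.2.1 method, but only a change-from-baseline table is listed, and the one scheduled post-baseline sample is optional. The ALP row is uninformative or inverted under either definition, although ALP rises still appear in the chemistry shift table. The plan should be corrected.

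**What to change.** 1. In SAP 9.2.1 and 9.2.2, add a shift from baseline to the post-baseline minimum beside the maximum, in Tables 14.3.4.1.2 and 14.3.4.2.2 and their open-label repeats. Coagulation needs no change. The minimum block may be limited to prespecified tests for which a low value has safety meaning.
2. Remove the stand-alone ALP row from Table 9-1 and keep ALP inside the combined DILI criterion.
3. State whether Table 14.3.4.2.3 counts notable or newly notable results.
4. Drafting: add ALT to the test list in SAP 9.2.2, since it is in the Protocol 6.2.2 panel. Reconcile the inequality signs for ALT/AST and bilirubin: Table 9-1's combined row uses >, while Protocol 6.2.1.3 and Listing 16.2.8.2.2 use ≥.

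The cost is SAP wording and one extra block in two tables and their repeats, from data already collected. The downside is chance Low values in about 3-9% of subjects per test under the assumptions above. A footnote should say that these are expected equally in both arms.

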9.2.2. Serum Chemistry

The following laboratory tests will be included: glucose, sodium, potassium, calcium, inorganic phosphate, total protein, albumin, blood urea nitrogen, creatinine, total bilirubin, alkaline phosphatase, aspartate aminotransferase, gamma-glutamyl transferase, and creatinine phosphokinase.

Summary tables presenting observed values and changes from baseline will be presented for serum chemistry tests with numeric values by treatment group for subjects in the Safety Analysis Set. Changes from baseline to each scheduled post-baseline visit will be presented. All chemistry data by subject will also be presented in a listing.

The clinical assessment of ‘Low’, ‘Normal’, or ‘High’ relative to the reference range will be summarized in shift tables comparing the baseline results to maximum value post-baseline for those subjects with results at both visits.

Results indicating liver-related abnormalities (i.e., ALT, AST, Total Bilirubin, and/or Alkaline Phosphatase) will also be summarized separately. A newly notable laboratory abnormality is defined as an abnormality observed post baseline that meets the notable criteria in [Table 9-1](#) and that did not exist at baseline. Subjects can still meet the criteria for a newly notable laboratory abnormality if the baseline value is missing. The table below displays the general variables and thresholds of interest. Subjects are considered to have notable laboratory abnormalities if his/her response falls within the specified definitions at least once during the treatment period.

Table 9-1: Notable Criteria for Laboratory Data Abnormalities – Liver Function Tests

Laboratory Variable	SI Units
AST	$\geq 3 \times \text{ULN}$
ALT	$\geq 3 \times \text{ULN}$
Total Bilirubin	$\geq 2 \times \text{ULN}$
Alkaline Phosphatase (ALP)	$\leq 2 \times \text{ULN}$
ALT or AST $> 3 \times \text{ULN}$ and total bilirubin $> 2 \times \text{ULN}$ and ALP $< 2 \times \text{ULN}$ (potential DILI or Hy's law case)	

All chemistry data by subject will be presented in a listing.

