6.2.1.3 Adverse Events of Special Interest

An AESI (serious or non-serious) is one of scientific and medical concern for which ongoing monitoring and rapid communication by the investigator to the sponsor can be appropriate. Adverse events of special interest for this study include liver tests that meet the criteria for potential drug-induced liver injury (DILI), in accordance with the US Food and Drug Administration (FDA) “Guidance for Industry-Drug-Induced Liver Injury: Premarketing Clinical Evaluation”.

Liver Tests and Stopping Criteria

The following 3 laboratory value criteria must be met for potential DILI, or “Hy’s Law”:

- An elevated alanine transaminase or aspartate transaminase laboratory value that is $\geq 3 \times \text{ULN}$
- An elevated total bilirubin laboratory value that is $\geq 2 \times \text{ULN}$

Fulcrum Therapeutics

Losmapimod

Protocol FIS-002-2019, Version 4.0 (COVID-19 Pandemic Emergency Amendment)

10 April 2020

- An alkaline phosphatase laboratory value that is $<2 \times \text{ULN}$

Study drug should be discontinued for subjects who meet the laboratory criteria for potential DILI as a result of within-protocol specific testing or unscheduled testing. This AESI must be reported to the sponsor within 24 hours of awareness. Further safety steps should be taken to closely observe and follow-up the event until resolution. These steps include, but are not limited to:

- Making every reasonable attempt to have the subject return to the clinic within 24 hours for repeat liver tests
- Obtaining a more detailed history of symptoms and prior or concurrent disease, concomitant medication use, alcohol use, recreational drug use, and special diets
- Repeating liver enzyme and serum bilirubin tests twice weekly. Frequency of retesting can decrease to once a week or less if abnormalities stabilize and the subject is asymptomatic
- Obtaining viral hepatitis serology
- Considering liver imaging and/or hepatology consultation

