Listing	16.2.8.1	Laboratory Results – Hematology	Safety Analysis Set	U	9.2.1	Safety		
Listing	16.2.8.2.1	Laboratory Results – Chemistry	Safety Analysis Set	R	9.2.2	Safety		
Listing	16.2.8.2.2	Laboratory Results of Subjects with Incidence of ALT/AST $\geq 3 \times$ ULN and Total Bilirubin $\geq 2 \times$ ULN and ALP $< 2 \times$ ULN	Safety Analysis Set	R	9.2.2	Safety		
Listing	16.2.8.3	Laboratory Results – Urinalysis	Safety Analysis Set	R	9.2.3	Safety		
Listing	16.2.8.4	Laboratory Results – Coagulation	Safety Analysis Set	R	9.2.4	Safety		
Listing	16.2.8.5	Vital Sign Results	Safety Analysis Set	U	9.3	Safety		
Listing	16.2.8.6	Electrocardiogram Results	Safety Analysis Set	U	9.5	Safety		

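### SAP Section 9.2.2 omits ALT from its chemistry list, and the combined potential-DILI row in Table 9-1 contradicts both the protocol and the SAP's own listing at the boundary values

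*SAP*

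**What the plan says.** **Chemistry tests.** Protocol Section 6.2.2 sets the serum chemistry panel, which ends with "aspartate aminotransferase, alanine aminotransferase, gamma-glutamyltransferase, creatine phosphokinase". Protocol Section 7.6.6 asks for descriptive summaries of how laboratory tests change during treatment. SAP Section 9.2.2 opens with an explicit list of included tests whose last items are "total bilirubin, alkaline phosphatase, aspartate aminotransferase, gamma-glutamyl transferase, and creatinine phosphokinase"; ALT is not in it. The section then plans change-from-baseline tables and low/normal/high shift tables. It adds: "Results indicating liver-related abnormalities (i.e., ALT, AST, Total Bilirubin, and/or Alkaline Phosphatase) will also be summarized separately". In Table 9-1, ALT has its own row at 3 x ULN or more.

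**Potential DILI.** Protocol Section 6.2.1.3 sets three laboratory criteria that must all be met. The first begins "An elevated alanine transaminase or aspartate transaminase laboratory value that is" and sets a floor of 3 x ULN, with the floor included. The second is total bilirubin of at least 2 x ULN, and the third is alkaline phosphatase (ALP) below 2 x ULN. The last row of SAP Table 9-1, labelled "potential DILI or Hy's law case", uses above 3, above 2 and below 2. SAP Listing 16.2.8.2.2 ("Laboratory Results of Subjects with Incidence of ALT/AST") uses at least 3, at least 2 and below 2. SAP Section 9.1 plans the number and percentage of subjects with an AESI, and refers to Section 9.2.2 for the liver criteria.

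**The concern.** Hepatotoxicity is the first risk discussed in Protocol Section 1.5. That section describes past transaminase elevations as few and generally mild, which is the range that a flag at 3 x ULN can miss. Tables of mean change and shift would show a modest upward drift in ALT on losmapimod relative to placebo. If ALT is absent from those tables, that comparison is not made.

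The second problem is one of definition. AESI incidence is a named secondary safety endpoint (Protocol Section 7.1.2, SAP Section 3.2.2), and potential DILI is the only AESI that the protocol names. If the SAP holds two rules for it, the liver table and the liver listing can disagree about the same subject, and it is unclear which rule the AESI summary follows.

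**Working it through.** The SAP states no figure to reproduce, so the check compares the two texts.

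**Step 1. Test lists** (Protocol Section 6.2.2 against SAP Section 9.2.2, grouped here for counting):

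| Group | Protocol | SAP |
|---|---|---|
| Sodium, potassium, calcium, phosphate | 4 | 4 |
| Glucose | 1 | 1 |
| Albumin, total protein | 2 | 2 |
| Urea nitrogen, creatinine | 2 | 2 |
| Bilirubin, ALP, AST, GGT | 4 | 4 |
| ALT | 1 | 0 |
| Creatine phosphokinase | 1 | 1 |
| **Total** | **15** | **14** |

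The SAP's spelling of the last test is taken as a typing variant of the protocol's. The difference is 15 - 14 = 1 test, ALT, and the SAP adds none of its own.

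**Step 2. Outputs affected.** SAP Section 15.8 plans Table 14.3.4.2.1 (change) and Table 14.3.4.2.2 (shift) under Section 9.2.2, each with a repeat on the pre-COVID-19 open-label set. Following the explicit list, these have no ALT row. Table 14.3.4.2.3 (notable liver results) does include ALT, through Table 9-1, but only from 3 x ULN upward. Listing 16.2.8.2.1 shows chemistry results by subject and does not compare arms.

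**Step 3. Potential-DILI rules.** Let a be ALT or AST, b total bilirubin and k ALP, all in multiples of ULN.

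- Protocol Section 6.2.1.3: a >= 3, b >= 2, k < 2
- SAP Listing 16.2.8.2.2: a >= 3, b >= 2, k < 2
- SAP Table 9-1, combined row: a > 3, b > 2, k < 2

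I evaluated all three rules on a grid with a = 2.9, 3.0, 3.1; b = 1.9, 2.0, 2.1; and k = 1.9, 2.0. That gives 3 x 3 x 2 = 18 combinations. They disagree in three:

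| a | b | k | Protocol | Listing | Table 9-1 combined row |
|---|---|---|---|---|---|
| 3.0 | 2.0 | 1.9 | yes | yes | no |
| 3.0 | 2.1 | 1.9 | yes | yes | no |
| 3.1 | 2.0 | 1.9 | yes | yes | no |

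The other 15 agree. A disagreement needs a exactly at 3 or b exactly at 2, with the remaining conditions met. The ALP condition is the same in all three rules.

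**Step 4. Later correction.** The SAP addendum says that it corrects typing errors in the SAP and protocol. The addendum sections available change neither the chemistry list nor the combined row.

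**The case against.** The strongest reply is that this is a drafting slip in a section that otherwise assumes ALT. Section 9.2.2 names ALT in the liver summary, in its own Table 9-1 row and in the combined row. The titles of the general chemistry tables carry no test list, and the table shells are in a separate document (SAP Section 4.1) that is not available here. A programmer might include ALT anyway, since Protocol Section 7.6.6 calls for laboratory summaries over time. This stands as an explanation and as a limit on certainty about the final tables. It does not change what the SAP's explicit list says.

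A reader might infer several stronger things that the documents do not support:

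- **That the ALT omission undermines the DILI or AESI outputs.** It does not reach them, because ALT is named in each liver-specific element of Section 9.2.2.
- **That an ALT rise below 3 x ULN would appear in no summary table.** Protocol Section 6.2.2 has clinically significant abnormal results recorded as adverse events, and treatment-emergent ones enter the tables of SAP Section 9.1.1. What is lost is the systematic comparison that does not depend on investigator judgement.
- **That ALT alone governs exclusion and stopping.** Exclusion criterion 6 also uses bilirubin and liver history. The potential-DILI criteria accept ALT or AST, together with bilirubin and ALP.
- **That the strict row will change the AESI count.** Investigators report AESIs to the sponsor under the protocol's criteria. The SAP does not say whether its count comes from those reports or from the combined row. The cross-reference from Section 9.1 makes this ambiguous, not established.

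**Conclusion.** Wrong as written, minor. There are two separate defects.

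First, the SAP's chemistry list omits one of the 15 protocol tests. As written, the general change and shift tables would not compare ALT between arms, while the liver-specific outputs keep it. This assumes that the tables follow the list, which the unavailable shells could confirm or contradict.

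Second, the SAP holds two potential-DILI definitions. The combined row of Table 9-1 conflicts with Protocol Section 6.2.1.3 and with Listing 16.2.8.2.2, and Section 9.1 refers to the section that contains the conflicting row. The effect is confined to values exactly at 3 x ULN for the transaminase or 2 x ULN for bilirubin. The documents give no basis for an expected number of such cases. Neither defect touches efficacy inference or data collection.

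**What to change.** 1. Add alanine aminotransferase to the test list in SAP Section 9.2.2, so that it enters the general change-from-baseline and shift tables. Check the table shells for the same omission.
2. Reconcile the combined row of Table 9-1 with Protocol Section 6.2.1.3 and Listing 16.2.8.2.2, so that table, listing and AESI summary use one tabulation definition. State in Section 9.1 whether the AESI count comes from reported events or from laboratory values. This concerns tabulation only and changes no clinical rule.

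The cost is two short edits and a clarifying sentence, which an addendum can carry. The protocol already collects every value needed. While Table 9-1 is open, its single-test ALP row also deserves a check: it counts values at or below 2 x ULN as notable, which would include normal results.
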